8.2.3. Action Taken with Study Medications

Action taken with study medications will be recorded on the AE eCRF page, as one of the following options:

- Dose Interrupted
- Dose Withdrawn
- Not Applicable
- Unknown

8.2.4. Outcome

Outcome of an AE will be recorded on the AE eCRF as follows:

- Recovered / Resolved

- Recovering / Resolving
- Recovered / Resolved with Sequelae
- Not Recovered / Not Resolving
- Fatal
- Unknown

8.3. Definition of a Serious Adverse Event

An SAE is any untoward medical occurrence that at any dose:

- Results in death
- Is life-threatening
- Requires inpatient hospitalization or prolongation of existing hospitalization
- Results in persistent or significant disability/incapacity, or
- Is a congenital anomaly/birth defect

Important medical events that may not be one of the above may be considered an SAE by the Investigator when, based upon appropriate medical judgement, are considered clinically significant and may jeopardise the subject, or may require medical or surgical intervention to prevent one of the outcomes listed above.

An AE is considered life-threatening if, in the opinion of either the Investigator or the Sponsor, its occurrence places the subject at immediate risk of death. It does not include an AE that, had it occurred in a more severe form, might have caused death.

8.3.1. Notification of a Serious Adverse Event

In order to meet the requirements for expedited reporting of SAEs meeting specific requirements to applicable regulatory authorities and institutional ECs, all SAEs, must be reported to CNS within 24 hours from the time the site investigational team first become aware of the event. This may be initially achieved by telephone, or by completing an SAE report form and e-mailing to CNS via the email address

[contact]

Initial notification of an SAE by telephone must be confirmed in writing 24 hours from the time the site investigational team first become aware of the event using the SAE report form as described above.

As further information regarding the SAE becomes available, such follow-up information should be documented on a new SAE report form, marked as a follow-up report, scanned and e-mailed to the address at the bottom of the report form.

Withdrawal from the study in the event of a SAE and therapeutic measures taken shall be at the discretion of the Investigator. A full explanation for the discontinuation from the study should be made in the subject's medical records and in the eCRF.

8.4. Clinical Laboratory Abnormalities and Other Abnormal Assessments as Adverse Events and Serious Adverse Events

Abnormal laboratory findings (e.g., clinical chemistry, haematology, and urinalysis) or other abnormal assessments (e.g., ECG and vital signs) per se are not reported as AEs. However, those abnormal findings that are deemed **clinically significant** or are associated with signs and/or symptoms must be recorded as AEs if they meet the definition of an AE (and recorded as an SAE if they meet the criteria of being serious) as described previously. Clinically significant abnormal laboratory or other abnormal findings that are detected after consent or that are present at baseline and worsen after consent are included as AEs (and SAEs if serious).

The Investigator should exercise his or her medical and scientific judgment in deciding whether an abnormal laboratory finding or other abnormal assessment is clinically significant. Usually, the abnormality should be associated with a clinically evident sign or symptom, or be likely to result in an evident sign or symptom in the near term, to be considered clinically significant. A clinically significant laboratory abnormality in the absence of clinical symptoms may jeopardize the subject and may require intervention to prevent immediate consequences. For example, a markedly low serum glucose concentration may not be accompanied by coma or convulsions, yet be of a magnitude to require glucose administration to prevent such sequelae.

8.5. Documenting Adverse Events

Any AE occurrence during the study must be documented in the subject's medical records in accordance with the Investigator's normal clinical practice and on the AE page of the eCRF. SAEs that occur during the study must be documented in the subject's medical record, on the AE eCRF, and on the SAE form.

The Investigator should attempt to establish a diagnosis of the event based on the signs, symptoms, and/or other clinical information. In such cases, the diagnosis should be documented as the AE (and SAE if serious) and not the individual signs/symptoms.

If a clinically significant abnormal laboratory finding or other abnormal assessment meets the definition of an AE, then the AE eCRF page must be completed as appropriate. In addition, if the abnormal assessment meets the criteria for being serious, the SAE form must also be completed. A diagnosis, if known, or clinical signs or symptoms if the diagnosis is unknown, rather than the clinically significant laboratory finding or abnormal assessment, should be used to complete the AE/SAE page. If no diagnosis is known and clinical signs or symptoms are not present, then

the abnormal finding should be recorded. If an SAE report is completed, pertinent laboratory data should be recorded on the SAE form, preferably with baseline values and copies of laboratory reports.

The SAE page should be completed as thoroughly as possible and signed by the Investigator before transmittal to the study Sponsor and CNS. It is very important that the Investigator provide an assessment of the causal relationship between the event and INP103 or placebo at the time of the initial report, as this will be useful for submissions to regulatory authorities.

8.6. Regulatory Authorities

The reporting of any SAEs to applicable regulatory authorities will be the responsibility of the Sponsor in compliance with applicable country regulations.

All SAEs must be reported to the HREC by the Investigator in accordance with their regulations.

8.7. Follow-Up of Adverse Events and Serious Adverse Events

All AEs and SAEs that are deemed related, possibly related or probably related to INP103 or placebo must be followed until resolution, until the condition stabilizes, until the event is otherwise explained, or until the subject dies or is lost to follow-up. The Investigator is responsible to ensure that follow-up includes any supplemental investigations as may be indicated to elucidate as completely as practical the nature and/or causality of the AE/SAE. This may include additional laboratory tests or investigations, histopathological examinations, or consultation with other health care professionals.

The Sponsor may request that the Investigator perform or arrange for the conduct of supplemental measurements and/or evaluations. If a subject dies during participation in the study or during a recognized follow-up period, the Sponsor should be provided with a copy of any post-mortem findings, including histopathology.

8.8. Pregnancy

Females who are pregnant, planning a pregnancy or lactating are to be excluded from the study. In the case of a pregnancy occurring during study participation or at any time during the 30 days following INP103 or placebo, it must be reported using a clinical trial pregnancy form. To ensure subject safety, each pregnancy must be reported to CNS within 5 days of the PI learning of its occurrence. The pregnancy should be followed up to determine outcome (including premature termination) and status of mother and child. The subject will be requested to provide written informed consent to enable collection of information pertaining to the outcome of the pregnancy. Pregnancy complications and elective terminations for medical reasons

must be reported as an AE or SAE. Spontaneous abortions must be reported as an SAE.

Any SAE occurring in association with a pregnancy brought to the Investigator's attention after the subject has completed the study and considered by the Investigator as possibly related to INP103 or placebo, must be promptly reported to CNS.

In addition, the Investigator must attempt to collect pregnancy information on any female partners of male study subjects who become pregnant while the subject is enrolled in the study. Pregnancy information must be reported to CNS as described above.

9. STUDY COMPLETION AND DISCONTINUATION

9.1. Subject Withdrawal

In accordance with applicable regulations, a subject has the right to withdraw from the study at any time and for any reason, without prejudice to his future medical care.

Subjects may be withdrawn from the study for any of the following reasons:

- Subject is unable or unwilling to continue participation in the study
- Adverse event (whether or not related to INP103 or placebo) that precludes further participation in the study in the judgment of the Investigator and/or Sponsor
- Protocol noncompliance
- Informed consent withdrawn
- The Investigator considers that it is in the subject's best interest for the subject not to continue participation in the study

If a subject is withdrawn because of an AE, the Investigator must arrange for the subject to have appropriate follow-up care until the AE is resolved or has stabilized. Unresolved AEs will be followed until the last scheduled follow-up visit or until the PI and Medical Monitor determine that further follow-up is no longer indicated. In addition to AEs, other reasons for removal of subjects from the study might include, but are not limited to, withdrawal of consent, administrative decision by the Investigator or the Sponsor, protocol deviation, or subject noncompliance.

If a subject asks or decides to withdraw from the study, all efforts will be made to complete and report the observations, especially the listed primary and secondary objectives, as thoroughly as possible up to the date of withdrawal. The primary reason for withdrawal will be identified and recorded on the appropriate eCRF, along with the date of withdrawal.

9.2. Subject Replacement

At least thirty-two subjects are planned for enrolment in the study. Subjects who consent but then do not receive INP103 or placebo for any reason may be replaced at the Sponsor's discretion. Subjects will not be replaced once dosed.

10. TERMINATION OR SUSPENSION OF THE STUDY

The Sponsor, Investigator, and the HREC reserve the right to terminate or suspend the study at any time; however, this should be discussed between the relevant parties beforehand and the reason for such decision recorded. Should this occur, all data available will also be recorded in the eCRFs. The Investigator should notify the relevant institutional HREC in writing of the study's completion or early discontinuation.

11. STUDY MONITORING AND DATA MANAGEMENT

11.1. Study Monitoring

The Sponsor has appointed Clinical Network Services (CNS) Pty Ltd to manage and monitor the study so as to assure them of the adequate conduct of the study and to act as the contact with the investigational site. A study monitor will be identified and will be responsible for liaison with, and support of, the investigational site.

The study monitor and regulatory authority inspectors are responsible for contacting and visiting the investigative site for the purpose of inspecting the facilities and, upon request, inspecting the various records of the study (e.g., eCRFs, essential documentation, and other pertinent data) provided that subject confidentiality is respected.

11.2. Access to the Study

The Sponsor, study monitor, HREC and applicable regulatory agencies may require access to all study documents held at the investigational site, as well as access to all members of the investigational site personnel. It is expected that such access would normally be arranged by agreement with the investigational site.

11.3. Source Document and Data Verification

The study monitor will visit the investigational site periodically where s/he shall:

- Meet with the Investigator and any other applicable site staff.
- Inspect the eCRFs throughout the study to verify adherence to the protocol; completeness, accuracy, and consistency of the data; and adherence to local regulations on the conduct of clinical research. The monitor should have access to subject medical records and other study-related records needed to verify the entries on the eCRFs. The Investigator will cooperate with the monitor to ensure that any problems detected in the course of these monitoring visits are resolved. The monitor will identify any data to be recorded directly on the eCRFs (i.e. no prior written or electronic record of data), and to be considered to be source data.
- Review the investigational site file and regulatory documentation.
- Collect copies of documents and completed eCRFs for use by the appointed data management group and retention by the Sponsor.
- Verify with reference to the INP103, benserazide, and placebo records, that drug products have been stored appropriately, and administered correctly, to eligible subjects.

All eCRFs should be maintained on the system with details of any changes logged accordingly.

11.4. Data Management

All data will be recorded in individual source documents. An eCRF will be created by the data management group for recording of the required data in the study database. All eCRF information is to be filled in by site staff. If an item is not available or is not applicable, this fact should be indicated. Blank spaces should not be present unless otherwise directed.

The study monitor will perform source data verification of data entered into the eCRF; when discrepancies are noted, the study monitor will raise queries for correction by the site. The data entered into the eCRF will be subject to data validation checks for consistency and completeness by the data management group. Data queries will then be generated and sent to the investigational site for response before the database is locked and released for statistical analysis.

12. STATISTICAL ANALYSES

This protocol section describes the statistical analyses as they are foreseen at the time of planning the study. A separate Statistical Analysis Plan (SAP) will be prepared prior to performing any unblinded analysis. The SAP will serve as a complement to the study protocol and supersedes it in case of differences.

12.1. Sample Size Calculation

Thirty-two (32) subjects (8 per dose group) are considered sufficient for assessment of safety and tolerability of SADs of INP103. However, we are proposing that Cohort 4 may enrol an additional 4 patients (for a maximum of 12) under the same randomization scheme (3:1). With at least eight subjects per group, the study has 80% power to detect an improvement of 13 points from baseline in MDS-UPDRS Part III scores within each dose level, assuming a standard deviation of 11 points, using a two-sided significance level of 0.05. This study is not powered for between-group comparisons of the pharmacodynamic endpoints.

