Study Objective(s):	
Primary Objective:
 
To compare the safety and tolerability of intranasal single doses of INP103 in the presence of decarboxylase inhibitor (DCI) to that of placebo in patients with Parkinson's Disease (PD) during an OFF episode.
 
Secondary Objectives:
 
 1. To characterize the pharmacokinetics (PK) of single doses of INP103 2. To explore the effect of single doses of INP103 versus placebo on motor function 3. To explore the PK/PD relationship of single doses of INP103 and motor function
Study Design:	
This is a Phase IIa randomized, double-blind, placebo controlled, single dose study to compare the safety, tolerability and PK/PD of intranasal L-dopa following administration of INP103 in the presence of L-dopa decarboxylase inhibitor (DCI) during an OFF episode.
 
Screening Assessment
 
Subjects will attend two pre-dosing visits: an initial Screening visit up to Day -21 (Visit 1), and a second screening visit (Visit 2), which may be repeated, between Day -20 and Day -1 (the day prior to Visit 3) during which dopaminergic responsiveness will be confirmed (see Screening Procedures below).

Randomization and Dosing

Subjects will be instructed not to take their usual PD medication from 22:00 pm on Day -1 (the day prior to dosing).

Subjects who arrive at the study site on Day 0 (or who were domiciled overnight) and are determined by the investigator to be in an ON state up to the scheduled time of dosing will not be dosed and will be excluded from further study participation.

Subjects will be enrolled into one of four dose treatment cohorts with at least 8 subjects per cohort. All subjects in Cohorts 1, 2 and 3 will receive oral DCI, benserazide hydrochloride, 25 mg at 60 ± 5 minutes before dosing with INP103 or placebo. Subjects in Cohort 4 will receive the DCI as carbidopa at 1/10th the dose of, and with, L-dopa via the POD device. At the discretion of the Sponsor, depending on rate of recruitment, cohort 4 may be over enrolled with a total of up to 12 subjects using the 3:1 randomization scheme. On Day 0 (Visit 3), subjects in each cohort will be randomized to receive treatments as follows:

Cohort	Treatment (Study Drug)
1	INP103 35 mg L-dopa (n=6); Placebo (n=2)
2	INP103 70 mg L-dopa (n=6); Placebo (n=2)
3	INP103 140 mg L-dopa (n=6); Placebo (n=2)
4	INP103 70 mg L-dopa/7.0 mg carbidopa (n=6, maximum 9); Placebo (n=2, maximum 3)

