7. TREATMENT COMPARISONS

7.1. Data Display Treatment and Other Sub-Group Descriptors

- All Placebo
- INP103 35 mg
- INP103 70 mg
- INP103 140 mg
- INP103 70 mg /7.0 mg carbidopa
- Overall

Note: All subjects randomized to placebo, from all cohorts, will be combined into a single placebo group (i.e. All Placebo Subjects).

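### Protocol 12.1 rests its within-dose power claim on eight subjects per dose group, but only six receive each dose in Cohorts 1 to 3, and whether 80% roughly holds depends on a test it does not name

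*Protocol*

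**What the plan says.** Protocol 12.1 opens with "Thirty-two (32) subjects (8 per dose group) are considered sufficient for assessment of safety and tolerability of SADs of INP103". It continues: "With at least eight subjects per group, the study has 80% power to detect an improvement of 13 points from baseline", within each dose level, "assuming a standard deviation of 11 points" and "using a two-sided significance level of 0.05". It closes by saying that the study is not powered for between-group comparisons of the pharmacodynamic endpoints.

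The design tables (Protocol synopsis, Protocol 1.4, SAP 4.2) give each of Cohorts 1 to 3 six INP103 and two placebo subjects. Cohort 4 has six INP103 and two placebo, or at most nine and three if the sponsor over-enrols. SAP 7.1 says "All subjects randomized to placebo, from all cohorts, will be combined into a single placebo group". The motor models in Protocol 12.5 and SAP 10.2 treat each dose and placebo as separate treatment groups, and state that their focus is the change within each group.

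SAP 4.1.1 repeats the count of eight per dose group, the 13 points, the SD and the 80%, but makes the improvement relative to placebo. It keeps the sentence about not being powered between groups. The statistical paragraphs of both synopses also give the placebo version, with eight subjects per cohort.

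**The concern.** The power sentence is about a dose level, yet its sample size is that of a cohort. Two of each eight subjects get no L-dopa from the device, and no planned motor analysis counts them in that dose's change. No dose level in Cohorts 1 to 3 can supply eight treated subjects. Six is the planned maximum there, since dosed subjects are not replaced and no dropout allowance is stated.

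This is the one power statement that matches the declared focus of the motor analysis. A reader who relies on it will expect more precision per dose than six subjects give. In a proof-of-concept study whose results may inform later studies (SAP 5.1), that could colour how a weak-looking dose is read.

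**Working it through.** **Inputs.** Change 13 points, SD 11 (taken as the SD of the change), two-sided 0.05, stated power 80%, stated n of 8: all Protocol 12.1. Treated per dose: 6 in Cohorts 1 to 3, 6 to 9 in Cohort 4 (design tables). Pooled placebo: 4 × 2 = 8, or 9 if Cohort 4 is filled.

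**1. Reproduce the printed figure.** One-sample t-test on change from baseline: non-centrality = (13/11)·√n, df = n − 1, power from the non-central t.

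| n | Non-centrality | df | Critical t | Power |
|---|---|---|---|---|
| 8 | 1.182 × 2.828 = 3.343 | 7 | 2.365 | 81.7% |
| 7 | 1.182 × 2.646 = 3.127 | 6 | 2.447 | 74.1% |
| 6 | 1.182 × 2.449 = 2.895 | 5 | 2.571 | **64.2%** |
| 9 | 1.182 × 3.000 = 3.545 | 8 | 2.306 | 87.2% |

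Eight is the smallest n that reaches 80%, so this calculation fits the printed effect, SD, level, n and power together.

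**2. Put in the treated number.** At n=6 the same test gives 64.2%, a difference of 81.7 − 64.2 = 17.5 percentage points. Solving for 80% power gives a detectable change of 12.7 points at n=8 and 15.8 points at n=6. The 95% half-width from a dose group's own data is 2.365 × 11/√8 = 9.2 points at n=8 and 2.571 × 11/√6 = 11.5 points at n=6.

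**3. Use the planned model instead.** The model mean for a dose uses a residual variance pooled over five groups. At one time point, 32 subjects less 5 group means and 1 covariate leave 26 df. With a common SD of 11 and n=6, the non-centrality stays 2.895 but the critical t falls to 2.056, so power is 79.6%. Allowing for estimation of the baseline slope brings it to 78.3%. A simulation of 10,000 runs gave 78.2% with no baseline correlation and 81.7% with a correlation of 0.3. At n=8 this basis would give 89.6%, so it does not explain the printed pairing of eight with 80%.

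**4. Check the placebo version (SAP 4.1.1, both synopses).** Two-sample t-test: non-centrality = 13 / (11·√(1/n₁ + 1/n₂)), df = n₁ + n₂ − 2.

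| Comparison | Power |
|---|---|
| 6 v 8 pooled placebo | 52.1% |
| 6 v 9 pooled placebo | 54.6% |
| 8 v 8 | 59.5% |
| 6 v 2 (own cohort only) | 23.2% |

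Pooling the variance does not rescue it: for 6 v 8 the non-centrality is 2.188, and on 26 df power is about 56%.

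**The case against.** The strongest reply is that 64% describes a test the trial will not report. SAP 10.1 only summarises the 30-minute change, and the within-dose intervals planned for the change scores are the model intervals of Protocol 12.5 and SAP 10.2. On those, six subjects give about 78 to 80%, so the printed power is roughly right at the correct n. This stands in part. A reader might infer that the trial has about a one in three chance of missing a true 13-point effect (100 − 64.2 = 35.8%). The documents do not support that for the planned intervals, where the corresponding figure is about 20 to 22%. The reply does not rescue the count of eight, and it assumes a common SD and a single time point.

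A reader might also infer that only the one-sample test at n=8 yields 80%. That is too strong. All 24 active against 8 placebo subjects gives 80.0%, and a one-sided one-sample t-test at n=6 gives 79.8%. The first contradicts both the per-dose wording and the eight per group; the second contradicts the two-sided level. The one-sample test at n=8 is the best fit to the printed terms, but how the sponsor reached the figure is not documented.

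Third, the SAP supersedes the protocol where they differ (Protocol 12), and the SAP words the claim against placebo. That is correct, but it makes the figure worse, and it conflicts with the SAP's own next sentence about between-group power.

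Finally, safety is primary, SAP 3.3 sets no formal hypotheses, SAP 10 calls the motor analysis exploratory, and the interim analysis has no stopping rule. This stands and limits the consequence.

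**Conclusion.** The point holds for the stated sample size and for the unnamed test. Protocol 12.1 claims power within each dose level on eight subjects, and the design supplies six in Cohorts 1 to 3 and six to nine in Cohort 4. On the calculation that best fits the printed terms, power for 13 points is 64.2% rather than about 80%, rising to 87.2% only if Cohort 4 reaches nine. On the model-based mean it is about 78 to 80%. So a 17-point loss of power is not established for the planned analysis; what is established is a wrong n, and a power figure that cannot be judged until the test is named. The placebo version in SAP 4.1.1 and both synopses is not supported on any per-dose two-sample basis checked.

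These figures assume that 11 is the SD of the change, that it is equal across groups where variance is pooled, and that no data are missing. The practical impact is modest: no subject number, analysis or decision rule depends on the sentence.

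**What to change.** 1. In Protocol 12.1 and SAP 4.1.1, replace the count of eight per dose group with six INP103 subjects per dose level (six to nine in Cohort 4), keeping 32 as the study total.
2. Name the test behind the power figure. For the dose group's own data, state about 64% for 13 points (80% for about 15.8 points; about 87% for 13 points with nine in Cohort 4). For the model-based within-group mean, state about 78%, with its common-variance assumption.
3. In SAP 4.1.1 and in the statistical paragraphs of both synopses, delete the comparison with placebo from the power sentence, or restate that power as about 52% (six against eight pooled placebo, two-sample t-test). If the within-dose claim is kept in the synopses, correct the n there too. Changing the n alone in SAP 4.1.1 would leave a between-group claim that the next sentence denies.

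The cost is wording in four places. No subjects are added and no analysis changes; the stated power becomes less favourable, or gains a stated assumption.
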